**Table 1. Keyboard Design Decision Rules**

Action	Number of evaluable subjects treated at the current dose level											
	1	2	3	4	5	6	7	8	9	10	11	12
Escalate if # of DLT $\leq$	0	0	0	0	1	1	1	1	2	2	2	2
Stay at same dose if # of DLT =	NA	NA	1	1	NA	2	2	2	3	3	3	3 or 4
De-escalate if # of DLT $\geq$	1	1	2	2	2	3	3	3	4	4	4	5
Eliminate if # of DLT $\geq$	NA	NA	3	3	4	4	5	5	5	6	6	7

Notes:

- "Eliminate" means that the current and higher doses are eliminated from the trial to prevent treating any future subjects at these doses because they are overly toxic. When a dose is eliminated, automatically de-escalate the dose to the next lower level. If the lowest dose is eliminated, stop the trial for safety. In this case, no dose should be selected as the MTD.
- If the current dose is the lowest dose and the rule indicates dose de-escalation, treat new subjects at the lowest dose unless the number of DLTs reaches the elimination boundary, at which point terminate the trial for safety.
- If the current dose is the highest dose and the rule indicates dose escalation, treat new subjects at the highest dose.

Based on accumulating data from the dose escalation phase, up to 2 Dose Expansion cohorts may be opened. Only one schedule will be evaluated in the expansion phase. Continuous toxicity monitoring (using sequential boundaries) will be used within each cohort. Accrual will be temporarily stopped if excessive numbers of subjects with  $\geq$  Grade 3 infusion related reactions (IRRs) are observed (i.e., if  $bn$  out of  $n$  subjects experience  $\geq$  Grade 3 IRRs as described in the table below). This is a Pocock-type stopping boundary that yields a probability of crossing the boundary of 0.05 at most when the rate of  $\geq$  Grade 3 IRRs is equal to the acceptable rate of 30%.

Number of subjects, n	1	2	3	4	5	6	7	8	9	10	11	12	13	14	15
Boundary, $bn$	-	-	-	4	5	5	6	6	6	7	7	8	8	9	9

Similarly, accrual will be temporarily stopped if excessive discontinuations due to toxicity are observed (i.e., if  $bn$  out of  $n$  subjects discontinue SL-279252 due to toxicity as described in the table below). This is a Pocock-type stopping boundary that yields a probability of crossing the boundary of 0.05 at most when the rate of discontinuation due to toxicity is equal to the acceptable rate of 15%.

Number of subjects, n	1	2	3	4	5	6	7	8	9	10	11	12	13	14	15
-----------------------	---	---	---	---	---	---	---	---	---	----	----	----	----	----	----

Boundary, bn	-	-	3	3	4	4	4	4	5	5	5	6	6	6	6
---------------------	---	---	---	---	---	---	---	---	---	---	---	---	---	---	---

### 3.2 Dose Escalation

Two or more dosing schedules for SL-279252 may be evaluated:

- **Schedule 1:** administering SL-279252 on days 1, 8 and 15 of the first 28-day cycle and then every 2 weeks thereafter on days 1 and 15 of each 28- day cycle beginning with cycle 2.
- **Schedule 2:** weekly dosing of SL-279252 on days 1, 8, 15 and 22 of each 28-day cycle.

A less frequent dosing schedule (e.g., once every three weeks or once every four weeks) may be investigated if safety data from Schedule 1 indicates that this approach is most prudent.

**Table 2. SL-279252 Dose Escalation Plan**

Dose Level	Dose of SL-279252 (mg/kg) a,b,c,d,e	Duration of Infusion e
Level 1	0.0001 mg/kg	5-30 minutes
Level 2	0.001 mg/kg	5-30 minutes
Level 3	0.003 mg/kg	5-30 minutes
Level 4	0.01 mg/kg	30 minutes (+/- 10 minutes)
Level 5	0.03 mg/kg	30 minutes (+/- 10 minutes)
Level 6	0.1 mg/kg	30 minutes (+/- 10 minutes)
Level 7	0.3 mg/kg	30 minutes (+/- 10 minutes)
Level 8	1.0 mg/kg	1 hour (+/- 15 minutes)
Level 9	3.0 mg/kg	1 hour (+/- 15 minutes)
Level 10	6.0 mg/kg	1 hour (+/- 15 minutes)

**a)** Dose escalation begins on Schedule 1: SL-279252 may be administered in the first cycle on days 1, 8, and 15 of the first 28-day cycle and then once every 2 weeks on days 1 and 15 of each 28-day cycle beginning at cycle 2.

**b)** Dose escalation on Schedule 2 may be tested: If Schedule 2 is opened, SL-279252 may be administered once weekly on days 1, 8, 15, and 22 of each 28-day cycle. The starting dose on schedule 2 will be at least one dose level below the current Schedule 1 dose level defined by the Keyboard design. If Schedule 2 is opened for enrollment, then enrollment on Schedule 1 will be halted.

**c)** Intermediate dose levels may be tested based on emerging safety data. The option to explore more than 10 dose levels on Schedule 1 or additional dose levels on Schedule 2 is also a possibility if safety allows. Escalations will not exceed half-log increments after dose level 2.

**d)** The actual body weight in kg will be used for dose calculation in all subjects whose body weight is  $\leq 100$  kg. For subjects with body weight  $> 100$  kg, the dose to be administered should be the same as that calculated for a subject weighing 100 kg.

**e)** Infusion time may change based on final drug volume needed for administration, safety and tolerability of the infusion for the subject, and/or observed safety findings during the study. Please refer to the Study Pharmacy Manual (SPM) for details.

**Evaluation of Schedule 1:** Initially, cohort size in Schedule 1 may be limited to 1 subject for enrollment until one of the following occurs: a  $\geq$  Grade 2 toxicity or DLT is observed (see Section 3.2.6 of protocol for DLT definitions) or DL 6 is reached; any of these scenarios will trigger

enrollment of  $\geq 3$  subjects in the current dose and dose level cohorts from that point forward. Multiple-subject cohorts will incorporate a minimum 3-day stagger between dosing the first and second subject at the same dose level, although this requirement may change based on emerging safety data as determined by the Safety Monitoring Committee (SMC). The incidence of DLT will be assessed over a period of 21 days during the first cycle of therapy on Schedule 1.

**Evaluation of Schedule 2:** If Schedule 1 is safe and tolerable, and pharmacodynamic effects are not present or detectable, this may suggest that a more frequent dosing schedule is warranted. In this event cohort enrollment on Schedule 2 will be instituted in lieu of Schedule 1.

The starting dose on Schedule 2 will be at least 1 DL lower than the current safe Schedule 1 DL defined by the Keyboard design. Dose escalation (or de-escalation) may then proceed based on a DL previously evaluated on Schedule 1 as shown in Table 1. For example, if 0.1 mg/kg (DL 6) is the current DL being evaluated on Schedule 1, then the starting dose on Schedule 2 will be 0.03 mg/kg (DL 5) or lower. A minimum of 3 subjects will be evaluated in each DL during dose escalation on Schedule 2. A minimum 3-day stagger between dosing the first and second subject at the same DL is required. The incidence of DLT will be assessed over a period of 28 days during the first cycle of therapy for Schedule 2.

**Evaluation of a Less Frequent Dosing Schedule:** If safety and pharmacodynamic data from Schedule 1 support exploration of a less intensive dosing schedule, then cohort enrollment on this as yet to be identified schedule will be instituted in lieu of Schedule 1.

After dosing has been completed at each dose level, safety, PK and PD data (as applicable) will be reviewed, and dose escalation decisions will be made by the SMC (composed of the Sponsor Representatives and the Principal Investigators). Dose escalation decisions will also take into consideration safety information beyond the DLT period from prior dose levels. In addition, if the SMC determines that, in the absence of DLTs, enrollment of additional subjects is required in order to better determine PK or safety, enrollment of an additional 3 subjects may be undertaken at 1 or more of the dose levels already studied. Should more than 3 subjects be accrued to a dose level for reasons other than DLT/toxicity, the decision to escalate further may be made after the first 3 subjects clear the DLT window period.

**Pharmacodynamic Cohorts:** The Sponsor, in consultation with the SMC, may elect to open a pharmacodynamic cohort in order to obtain additional pharmacodynamic data from a total of approximately 6 additional subjects at one or more dose levels that have previously completed evaluation for safety and has not exceeded the MTD. Subjects enrolled in the pharmacodynamic cohort will not inform dose escalation decisions but the pharmacodynamic information gathered from these additional subjects may inform selection of doses for further evaluation in dose expansion.

### 3.3 Dose Expansion

Based on accumulating data from the dose escalation phase, including safety, PK, pharmacodynamic and anti-tumor activity, up to two Dose Expansion Cohorts may be opened for enrollment. The expansion cohorts could potentially begin enrollment prior to the end of dose escalation. A minimum of 6 subjects must be evaluated at the dose level to be expanded to confirm

safety and tolerability prior to expansion. One or two doses of SL-279252 (on the same schedule, i.e., only one schedule will be evaluated in the expansion phase) may be expanded.

### **3.4 Study Assessments and Procedures**

The detailed study assessments and procedures are described in Section 6 of the protocol.

## **4. SAMPLE SIZE**

If only Schedule 1 is evaluated, the maximum planned sample size is 42 for dose escalation. If Schedule 1 and 2 are both fully evaluated in dose escalation, the maximum planned sample size is 57. If pharmacodynamic cohorts are opened in dose escalation, the maximum sample size is 48 if schedule 1 is fully evaluated or 63 if Schedule 1 and 2 are fully evaluated. The sample size in each Expansion Cohort is ~15 subjects. Overall, the total sample size estimate for this study is ~ 78 subjects assuming only Schedule 1 is evaluated and pharmacodynamic cohorts are opened and ~93 subjects if both Schedule 1 and 2 are fully evaluated and pharmacodynamic cohorts are opened.

## **5. GENERAL ANALYSIS CONSIDERATIONS**

### **5.1 Reporting Conventions**

The statistical analyses will be reported using summary tables, figures, and data listings. The International Conference on Harmonisation (ICH) numbering convention will be used for all tables, listings, and figures.

Data from all participating sites will be pooled prior to data summary or analysis. It is anticipated that subject accrual will be spread thinly across sites and summaries of data by site will not be informative and therefore, will not be provided.

Unless specified otherwise, all summary tables will be presented by dose schedule/level for all subjects in the analysis population. Subjects from dose escalation and pharmacodynamic cohorts will be pooled. Summaries will be provided for each expansion cohort separately if data warrants.

All individual subject data listings will be presented by dose level, dose schedule and subject, unless specified otherwise. Data from all assessments, whether scheduled or unscheduled, will be included in the listings. Listings will present the data in their original format (without any imputation), unless specified otherwise.

Summaries by planned time point will include data from scheduled assessments and all data will be reported according to the nominal visit for which it will be recorded (i.e., no visit windows will be applied). Unscheduled data, when summarized, will be included only in calculation of the maximum or minimum value over time such as worst-case post-baseline. If multiple assessments are reported on the same date for the same scheduled planned time, the worst-case result will be analyzed.

Continuous variables will be summarized with means, standard deviations, medians, minimums, and maximums. The precision of the original measurements will be maintained in summaries and listings, when possible. Generally, means and medians will be presented to one more decimal place than the raw data, and the standard deviations will be presented to two more decimal places than the raw data.

Categorical variables will be summarized by counts and by percentages of subjects in the corresponding categories. Percentages are routinely based on the total number of the specified population N if not otherwise specified. For frequency counts, categories whose counts are zero will be displayed for the sake of completeness. For example, if none of the subjects discontinue due to “lost to follow-up,” this reason will be included in the table with a count of 0. Categories with zero counts will not have zero percentages displayed.

All confidence intervals (CIs) will be constructed at the 95% confidence level, unless specified otherwise.

All analyses and tabulations will be performed using SAS® v9.4 or above.

## 5.2 Data Handling

The following sections provide a general description of the derived and transformed variables used to describe and analyze the data.

### 5.2.1 Missing Data

Missing data occurs when any requested data is not provided, leading to blank field on the collection instrument. Answers such as “Not applicable”, “Not evaluable”, etc. are not considered to be missing data and should be displayed as such.

For the time to event endpoints including duration of response (DOR), progression free survival (PFS), and overall survival (OS), the missing data handling method will be censoring. Censoring mechanisms for these endpoints are described in Section 8.

The length of study treatment for each subject will depend on the safety, tolerability and efficacy of the treatment, so the duration of treatment will vary across subjects. Similarly, the duration of follow up for survival will also vary. All time to event endpoints will be analyzed using suitable statistical methods.

In the event that the study is prematurely discontinued, the study team will review the data to assess which statistical analyses are still considered appropriate.

### 5.2.2 Baseline and Change from Baseline

Unless otherwise specified, the baseline value is defined as the last value obtained on or before the date and time of the first SL-279252 dose on Cycle 1 Day (C1D1). Post-baseline values are defined as value obtained after the first dose of SL-279252.

Change from baseline is calculated as:

- Post-baseline value - baseline value

The percent change from baseline is calculated as:

- $(\text{Post-baseline value} - \text{baseline value}) * 100 / \text{baseline value}$

If either baseline or post-baseline value is missing, the change from baseline and percent change from baseline will be missing.

### 5.2.3 Study Day, Duration, and Time from Event

The reference date for age calculation is the date of consent form signed as age is an eligibility requirement. The reference date for safety, efficacy and other data analyses is the date of the first dose.

- **Study Day** – Study Day 1 is defined as the date of the first dose; the day before the first dose is defined as Study Day -1. There is no study day 0. For a given event date, Study Day is calculated relative to the date of the first dose of study drug.

Study Day = [Event Date – First Dose Date] (in days) + 1 day,  
where the event date is on or after the first dose date.

Study Day = [Event Date – First Dose Date] (in days),  
where the event date is before the first dose date.

- **Duration (Days)** – A duration is calculated as the stop date minus the start date plus one.

Duration (days) = [Stop Date – Start Date] (in days) + 1 day.

- **Time since an event** - Time since an event (e.g. time since initial diagnosis) is calculated as the reference date minus the event date. For time since initial diagnosis, the reference date is the first dose of study treatment.

- **Time to an event** - Time to an event (e.g. time to response, PFS, OS) is calculated as the event date minus the reference date+1. For time to response, PFS and OS, the first dose of study treatment is the reference date.

To convert days to months, divide the number of days by 30.4375 (365.25/12) and round to one decimal place.

### 5.2.4 Imputation of Partial Date

In general, imputed partial dates will not be used to derive study day or duration variables, unless otherwise specified. No partial dates imputation will be performed for time to event endpoint analysis. Any imputed partial data will be flagged in the analysis datasets to indicate the level of imputation. Imputed dates will not be displayed in the data listings.

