s. **Follow-Up:** All subjects will be contacted after discontinuing study therapy to collect survival status. Subjects should be contacted every 3 months (+/- 14 days) until death, withdrawal of consent or subject is lost to follow-up. Contact may include clinic visit, telephone contact, email or mail to document survival status.

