**Table 5. Summary of Censoring Guidelines for PFS based on iRECIST**

Situation	Date of PD/Death or Censoring	PFS Outcome
Documented iCPD or death	Date of the initial iUPD that is confirmed or death, whichever comes first	Event (unless the censoring rule specified below)
iUPD and if iUPD is not confirmed and there is no subsequent iSD, iPR or iCR 	Date of the last iUPD	Event (unless the censoring rule specified below)
Death or iUPD immediately after $\geq 2$ consecutive missed or non-evaluable disease assessments  as per the protocol specified assessment schedule	Date of last evaluable disease assessment prior to missed or non-evaluable assessments, or the first dose of investigational product, whichever occurred last	Censored
No iCPD or death at time of analysis or lost to follow-up	Date of last evaluable disease assessment	Censored
No tumor assessment at baseline OR No tumor assessment post-first dose, and no death prior to second scheduled post-baseline disease assessment	Date of first dose	Censored

 If iUPD is not confirmed and there is no subsequent iSD, iPR or iCR, then the iUPD date should still be used as progression event for PFS in the following scenarios: if the subjects stop study treatment because they were not judged to be clinically stable, or no further response assessments are done; the next timepoint responses are all iUPD, and iCPD never occurs; or the subject dies from their cancer.

 Two or more consecutive assessments is defined as  $\geq 16+1$  weeks for the first 6 months or  $\geq 24+1$  weeks for 6-24 months (two disease assessments as per protocol plus a one week visit window to allow for a late assessment) after the last evaluable post-baseline disease assessment. If a subject has two or more consecutive missed or non-evaluable assessments followed by an assessment showing no radiologic disease progression, then the assumption will be that the subject did not progress during the missed or non-evaluable assessments.

The median and quartiles of PFS and their 95% CIs will be assessed using the Kaplan-Meier method and Brookmeyer and Crowley (1982) method, respectively. The proportion of subjects

that are progression free and alive at 12, 24, 48, 72, 96 weeks and other timepoints of interest and associated 95% CI will be estimated using the Kaplan-Meier method.

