## **8.10 Overall Survival**

OS is defined as time from the first day of treatment to the date of death. A subject alive at the end of study or lost to follow-up will be censored for OS at the last date when the subject was known to be alive.

The median and quartiles of OS and their 95% CIs will be assessed using the Kaplan-Meier method and Brookmeyer and Crowley (1982) method, respectively. The proportion of subjects alive at 12, 24, 48, 72, 96 weeks and other timepoints of interest and associated 95% CI will be estimated using the Kaplan-Meier method. Summary of OS will be provided for the All Treated population for solid tumors and lymphoma, respectively, if data warrants.

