### **8.11.2 Handling of Dropouts or Missing Data**

For the efficacy variables no imputations will be made for missing values except as noted in considering a NE response.

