### 11.2 Adverse Events

AE terms on the eCRFs will be mapped to preferred terms (PT) and system organ classes (SOC) using the Medical Dictionary for Regulatory Activities (MedDRA) Version 26.0.

Drug-related AEs are defined as AEs with relationship to study treatment being related or possible related. A worst-case scenario approach will be taken to handle missing data, i.e. AEs with missing relationship to study drug will be treated as drug-related AEs.

All AEs with onset dates on or after the first dose of study treatment are defined as treatment-emergent adverse events (TEAEs). Only TEAEs will be included in AE tables.

If both the start and end dates are completely missing, the AE will be considered treatment-emergent. Partial start and end dates will be imputed similarly as described for prior and concomitant medications in Section 7.7 for the purpose of determining treatment-emergent and AE duration.

The AE summaries that are displayed by SOC and PT will be ordered by descending order of incidence of SOC and PT within each SOC based on the total number of subjects. The following summaries will be presented.

- Overall Summary of TEAEs.
- Subject incidence of all TEAEs, drug-related TEAEs, immune related TEAEs by MedDRA SOC, PT and maximum toxicity grade. At each level of subject summarization, a subject is classified to the highest toxicity grade if the subject reported one or more events.
- Subject incidence of all TEAEs, serious TEAE, drug-related TEAEs, and drug-related serious TEAEs by PT.
- Subject incidence of all TEAEs with toxicity grade 3 or 4 by PT.
- DLT for dose escalation cohorts.
- Subject incidence of all TEAEs leading to drug interruptions and permanent discontinuation of study treatment by PT.
- Subject incidence of immune related TEAEs leading to permanent discontinuation of study treatment by PT.
- Subject incidence of deaths within and outside of 30 days of last dose and cause of death.

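### A death known only to month or year has no computable OS time under the SAP's ban on partial-date imputation, and no rule keeps it as an event

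*SAP*

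**What the plan says.** SAP Section 5.2.4 sets the rule: "No partial dates imputation will be performed for time to event endpoint analysis". Section 8.11.2 adds: "For the efficacy variables no imputations will be made for missing values except as noted in considering a NE response".

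Section 5.2.3 gives the calculation: "Time to an event (e.g. time to response, PFS, OS) is calculated as the event date minus the reference date+1". For DOR, PFS and OS, Section 5.2.1 says that "the missing data handling method will be censoring" and refers to Section 8 for the mechanisms. There, Section 8.10 says: "A subject alive at the end of study or lost to follow-up will be censored for OS", at the date last known alive. In Table 5 (PFS by iRECIST), the row for subjects without an event reads "No iCPD or death at time of analysis or lost to follow-up". Table 6 (PFS by RECIST 1.1) has the parallel row. None of these places mentions a death whose date is incomplete.

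On data collection, the follow-up footnotes to the protocol's schedules of assessments require survival contact every 3 months (+/- 14 days) once study therapy has stopped: "Contact may include clinic visit, telephone contact, email or mail to document survival status".

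The SAP does impute partial dates elsewhere: cancer history (Section 7.4), medications (Section 7.7) and adverse events (Section 11.2).

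**The concern.** A relative or a local physician who reports a death by telephone or mail may know only the month or the year. The event is then certain and only its exact date is missing. Under Section 5.2.4 the date may not be completed, so the formula in Section 5.2.3 yields nothing. The programmer must choose between censoring the subject at the last contact before death and removing the subject. Both choices are triggered by the fact of death, so the loss is informative and inflates the survival curve. The planned OS medians and 12- to 96-week survival proportions, and the Kaplan-Meier figure, would all carry that bias, from a rule that looks cautious.

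**Working it through.** **Tracing one partly dated death through the SAP**

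1. Section 5.2.3 requires an event date. Month or year alone gives no event time.
2. Sections 5.2.4 and 8.11.2 forbid completing it.
3. Section 5.2.1 points to censoring as the general method.
4. Section 8.10 allows OS censoring for two groups only, alive or lost to follow-up. A subject known to be dead is in neither.
5. Tables 5 and 6 date a death event by the date of death and have no row for a partial one.

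No rule retains the death as an event, and Sections 5.2.1 and 8.10 conflict on what to do instead. Section 12 of the SAP does not address it.

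**One subject in a small cohort**

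Take 15 subjects (the size of one expansion cohort), assume 10 deaths by week 48 and no other censoring.

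- All deaths counted: 5/15 = 33.3%.
- Third death censored in its place in the order: 13/15 × 5/12 = 36.1%.
- Tenth death censored in its place: 6/15 = 40.0%.
- One such subject dropped: 5/14 = 35.7%.

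**Average bias**

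The documents state no OS median, event count or partial-date rate, so there is no planned figure to reproduce. A large-sample Kaplan-Meier simulation (400,000 subjects) used these assumptions: exponential OS with median 6 or 12 months; administrative censoring uniform on 3 to 32 months, from the minimum follow-up in Protocol Section 3.13 and the study length in Section 4.5; a random 2-20% of deaths partly dated; and last contact on a 3-month grid. Estimated 48-week OS, with the Kaplan-Meier median in months in brackets:

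| Deaths partly dated | True median 6: censored | True median 6: dropped | True median 12: censored | True median 12: dropped |
|---|---|---|---|---|
| 0% | 27.9% (6.0) | 27.9% (6.0) | 52.8% (12.0) | 52.8% (12.0) |
| 2% | 28.5% (6.1) | 28.2% (6.0) | 53.4% (12.2) | 53.2% (12.1) |
| 5% | 29.5% (6.3) | 28.5% (6.1) | 54.4% (12.6) | 53.7% (12.3) |
| 10% | 31.2% (6.5) | 29.1% (6.2) | 56.0% (13.2) | 54.6% (12.7) |
| 20% | 34.8% (7.2) | 30.6% (6.4) | 59.5% (14.7) | 56.7% (13.5) |

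At 5% and 10%, censoring adds 29.5 − 27.9 = 1.6 and 31.2 − 27.9 = 3.3 points (median 6), or 1.6 and 3.2 points (median 12). Dropping adds 0.6 and 1.2, or 0.9 and 1.8 points. A separate simulation with 48 subjects, median 35 weeks and 10% partly dated gave 38.5% rising to 42.0% (censored) or 40.4% (dropped).

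**Scale against sampling error**

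With a true median of 6 months, the central 95% range of the Kaplan-Meier median is 3.6-9.3 months for 42 subjects and 4.5-7.9 months for 93. With a true median of 12 months, it is 7.4-19.3 and 8.8-16.6 months.

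**Effect of the remedy**

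With the month known, mid-month imputation bounded below by the last contact returned 27.9% and 52.8%, and medians of 6.0 and 12.0 months, at every rate from 2% to 20%. The year-only case was not simulated.

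**The case against.** The best counter-argument is that the harm is hypothetical and small. Nothing shows that the eCRF accepts a partial death date or that one occurred. Deaths handled as SAEs reach the sponsor within 24 hours of site awareness, adverse events are followed for 90 days after the last dose unless new anti-cancer therapy starts, and Protocol Section 14.2 requires data checks and site queries before lock. This stands as a limit on frequency. It does not supply a rule for a death first learned of through a late survival contact, where a query may bring no better date.

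Four stronger readings are tempting and go too far:

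- A reader might infer that the SAP orders such deaths to be censored as alive. It does not. Section 8.10, read literally, excludes that, and the outcome is left to the programmer.
- A reader might infer that PFS and DOR are overstated to the same degree. A partly dated death matters there only if it is the first event. Imaging continues until progression or new therapy, so many late deaths follow a dated progression. Tables 5 and 6 also already censor a death that comes straight after two or more missed assessments. All the figures above are for OS.
- A reader might extend the point to the safety table described as "Subject incidence of deaths within and outside of 30 days of last dose and cause of death". That is an incidence count, so the ban on time-to-event imputation does not reach it.
- A reader might take survival status to be collected only every 3 months. That interval applies after study therapy stops. During treatment, dosing visits are frequent.

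**Conclusion.** The gap is real for OS: a stated rule, followed as written, cannot keep a known but partly dated death as an event, and the two sections that might resolve it disagree. The bias in estimated survival after such deaths is upward whether the subject is censored or dropped. Its size depends on a rate that the documents do not give. At an assumed 5-10% of deaths it is roughly 1.5-3.5 points in 48-week OS with censoring, and less with dropping. That rests on partial dates occurring at random and on the assumed survival and censoring patterns. It is small against sampling error at the planned sample sizes, although a single subject can visibly move the curve of a 15-subject cohort.

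Protocol Section 2 makes OS and PFS exploratory, and there is no comparator arm. MTD, DLT, ORR and CBR are not affected. This is worth correcting because the remedy is simple. It does not threaten the study's main conclusions.

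**What to change.** In SAP Section 5.2.4, exempt date of death from the ban:

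- Day missing: use the middle of the month.
- Month also missing: use the midpoint of the possible window.
- Always later than the date last known alive, and no later than the date the death was reported or the data cut-off.
- Flag the imputed date and count the death as an event.

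Amend Sections 5.2.1, 8.10 and 8.11.2 to match; otherwise they would still contradict the exception. The existing PFS rule on deaths after missed assessments can stay as it is.

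Add a sensitivity analysis that places each such death at its earliest and then its latest possible date. It should also cover completely missing death dates, whose window runs from last known alive to report or cut-off.

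The cost is a few sentences and a little programming. The downside is a dating error of about two weeks when only the day is missing, and of up to about half the interval since last known alive when the month is missing too. The sensitivity bounds show both. The change should be made before Database Freeze, because SAP Section 1 says its decisions precede that point and that departures must be documented in the study report.
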